7.1 Study Subjects

7.1.1 Disposition of Subjects

Subject disposition will be summarized using a STROBE like flow diagram with follow-up compliance reported at 3 and 6 months.

7.1.2 Clinical Investigation Plan (CIP) Deviations

Protocol deviations will be reported descriptively using counts and will be reported for each type by site and for the overall study.

7.1.3 Analysis Sets

Full Analysis Set

The full analysis set will include all participants and be used for all analyses. Visits outside of visit windows will be assigned to the nearest window. If a participant is missing data for a specific analysis, they will be excluded for that analysis. Within the analysis set, the grouping participants into the healthy, PAD (definitions 1 and 2), and CLI groups are defined in section 4.1.1.1.

7.2 General Methodology

Data analysis will be performed by Medtronic employed statisticians/programmers. All statistical analyses will be generated using SAS version 9.4 or later or R version 4.1 or later software. Demographic and baseline characteristics will be summarized descriptively and will include age, gender, ethnicity, race, body mass index and hemodynamic measures (ABI, TBI, and acceleration time from the FlowMet-R device). For continuous variables, descriptive statistics will be presented including the number of

subjects with the measurement, mean, standard deviation, median, minimum and maximum. For categorical variables, descriptive statistics will include the number with the characteristic, the number evaluated, and the percentage.

Subject enrollment and accountability, visit attendance, and end of study status will be displayed using a STROBE like diagram and descriptive statistics, as appropriate. For each study visit, the following information will be tallied: completed visits, missed visits, deaths (if any), study withdrawals, and lost to follow-up. Compliance with study visits will be summarized as the percent of subjects available at each visit.

Missing data for endpoints may result from clinical assessments that were unable to be performed or data missing from the FlowMet device. These missing values will be excluded from summaries and analyses. In general, efforts will be made to minimize missing data and imputation of missing data will not be performed.

The objectives are not hypothesis-driven and therefore their results will be presented descriptively with no adjustments for multiple comparisons.

The value from the predictive model from the FlowMet-R measurements will be derived by the Research and Development team and will consist of the acceleration time.

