7.4 Handling of Missing, Unused, and Spurious Data and Dropouts

Data that is missing or incomplete will not be imputed. Complete case data will be used where all data for the respective analysis is available for a patient or visit.

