7.6 Demographic and Other Baseline Characteristics

Demographic and baseline characteristic variables will be summarized descriptively. The mean, standard deviation, median, minimum, 1st quartile, 3rd quartile, maximum, and the corresponding number of participants or limbs will be reported for continuous variables. The percentage and count will be reported for categorical and binary variables.

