7.7 ABI and TBI Values

The ABI and TBI for a limb will use the value in the data. If the ABI or TBI is missing, it will be derived from the ankle and brachial pressures or the toe and brachial pressures, respectively.

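### The SAP gives no value for a valid pulseless recording; if acceleration time needs a pulse, its exclusion rules drop limbs because they are severely diseased

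*SAP*

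**What the plan says.** **Recording.** Protocol 9.6 lets the operator confirm signal quality either by a pulse or, with complete occlusion, by a steady flat line. It warns that advanced disease can damp or abolish the waveform. It then accepts a near-flat graph without major motion artefact. Protocol 12.1.2 says a pulse appears only when digital flow is sufficient, and it allows flow amplitude as well as waveform features as model inputs.

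**Predictor.** SAP 7.2 narrows this to one quantity: the model value "will be derived by the Research and Development team and will consist of the acceleration time". SAP 7.8 repeats that the Research and Development team derives it from device data, and SAP 7.10.1 uses it for every primary ROC curve. No section defines it or says what a flat trace receives.

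**Missing data.** SAP 7.2 names "data missing from the FlowMet device" as one source of missing values and continues: "These missing values will be excluded from summaries and analyses". SAP 7.1.3 says "If a participant is missing data for a specific analysis, they will be excluded for that analysis". SAP 7.4 says "Complete case data will be used where all data for the respective analysis is available for a patient or visit". There is no imputation.

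**Unit.** The analysis itself is by limb. SAP 7.7 begins "The ABI and TBI for a limb will use the value in the data", SAP 7.8 merges by subject, visit and limb, and accuracy in SAP 7.10.1 is a count of limbs.

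**Reporting.** SAP 7.2: "For each study visit, the following information will be tallied: completed visits, missed visits, deaths (if any), study withdrawals, and lost to follow-up". For baseline variables, SAP 7.6 adds that "the corresponding number of participants or limbs will be reported for continuous variables", and SAP 7.2 lists acceleration time among the baseline measures.

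**The concern.** The protocol's rule on what counts as a valid recording and the SAP's rules on what counts as missing are never connected. A flat trace from an occluded limb is a measurement: the device was placed properly and found no pulse. If acceleration time can be computed only from a pulse, that limb has no predictor value. Under the SAP it then falls in the same class as a recording spoiled by motion or light level. The loss would be caused by the condition being diagnosed.

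Three things are at stake. First, the primary AUC, sensitivity, specificity and accuracy would apply only to limbs that still have a measurable pulse, while the stated objective is diagnosis of PAD and CLI in general. Second, SAP 7.1.3 excludes the participant. Read literally, one flat limb could also remove the other limb, although the analysis is by limb. Third, the planned tables would not explain the loss. A baseline count of acceleration time would show a shortfall, but not its cause, its split by disease group, or what was lost at the 3 and 6 month visits.

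**Working it through.** **1. The plan's own figure.** SAP 6 plans 100 CLI limbs and 160 control limbs at alpha 0.05 and power 0.80, with the CLI AUC allowed to fall 0.20 below the pilot value of 0.80. Take AUC 0.60, ratio R = 160/100 = 1.6, a two-sided test against 0.5, and the binormal variance V = 0.0099 exp(-a²/2)[(5a² + 8) + (a² + 8)/R], where a = 1.414 × the normal quantile of the AUC. Then n = [1.96√V(0.5) + 0.842√V(0.6)]² / 0.10² = 100.7. That gives 101 CLI and 162 control limbs, so the planned 100 and 160 are reproduced. They are not in dispute and serve only as a base.

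**2. Inputs for the illustration.** A = complete-case AUC = 0.80. This is the pilot CLI value in SAP 6, from a model not identified as acceleration time. f = share of CLI limbs that are flat: not in the documents, assumed 5% to 30%. g = share of negatives that are flat: also not in the documents, first taken as 0.

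**3. No flat negatives.** Most-diseased rank: (1 - f)A + f. Least-diseased rank: (1 - f)A.

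| f | Most diseased | Least diseased |
|---|---|---|
| 5% | 0.95 × 0.80 + 0.05 = 0.81 | 0.95 × 0.80 = 0.76 |
| 10% | 0.90 × 0.80 + 0.10 = 0.82 | 0.90 × 0.80 = 0.72 |
| 20% | 0.80 × 0.80 + 0.20 = 0.84 | 0.80 × 0.80 = 0.64 |
| 30% | 0.70 × 0.80 + 0.30 = 0.86 | 0.70 × 0.80 = 0.56 |

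**4. The same question in reverse.** If 0.80 is instead the all-limb AUC with flat limbs ranked most diseased, complete-case analysis reports (0.80 - f)/(1 - f). This is 0.778, 0.750 and 0.714 at f = 10%, 20% and 30%.

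**5. Flat negatives.** With most-diseased rank the all-limb AUC is (1 - f)(1 - g)A + f(1 - g) + 0.5fg. At f = 20% this is 0.84(1 - g) + 0.1g = 0.84 - 0.74g. It gives 0.803 at g = 5% and 0.766 at g = 10%. It equals the complete-case 0.80 at g = 0.04/0.74 = 0.054. Above about 5.4% flat negatives, dropping flat limbs raises the reported AUC instead of lowering it.

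**6. Why g may not be zero.** SAP 4.1.1.1.1 defines CLI by rest pain and wounds together, verified by TBI, and SAP 7.12 classifies limbs whatever their enrolled cohort. An occluded limb that lacks one of these features is therefore CLI-negative. SAP 5 measures the healthy cohort once only, so the 160 controls are absent at 3 and 6 months and negatives then come from the PAD cohort. Steps 3 to 5 speak to baseline only.

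**The case against.** The strongest reply is that the harm rests on a definition nobody outside the Research and Development team has seen. No section says that acceleration time needs a pulse. The derivation may already give a flat trace a value, and a damped waveform may still yield one. If so, no limb is lost and only a reporting gap remains. This stands, and the point is conditional for that reason. It does not remove the need to state the rule, because an unstated rule can be chosen after results are seen.

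The flat rate is also assumed. Moreover, some pulseless limbs may lack a TBI, since Protocol 9.7.1 detects the toe waveform optically. Such limbs might be unclassifiable however acceleration time is handled. That is a fair limit on the illustration, which treats every flat limb as a confirmed CLI limb.

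Three stronger readings are tempting, and the documents support none of them:

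- A reader might infer that the AUC is biased in a known direction. Steps 3 and 5 show that it can move either way.
- A reader might infer that the primary conclusion would change. SAP 7.10.1 requires the interval to exclude 0.5 at all three visits. The illustration covers baseline only and says nothing about the other two.
- A reader might infer that the loss would be invisible. SAP 7.2 and 7.6 would show a baseline shortfall; what they lack is cause, disease group and follow-up visits.

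SAP 7.2 also calls the objectives descriptive. That softens the consequence, but AUC, sensitivity and specificity are themselves the primary endpoints in SAP 4.1.1.1.

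**Conclusion.** The omission is certain: the SAP has one predictor, does not define it, and has no rule for a recording that the protocol accepts as valid. The consequence is conditional. If acceleration time needs a pulse, following SAP 7.1.3, 7.2 and 7.4 as written would drop limbs on account of disease severity and restrict every primary result to limbs with a pulse. The inconsistency between participant, patient or visit, and limb stands whatever acceleration time turns out to be.

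The size cannot be stated. At baseline, with a complete-case AUC of 0.80, 20% of CLI limbs flat and no flat negatives, the all-limb AUC lies between 0.64 and 0.84 according to how flat limbs are ranked. The range is 0.76 to 0.81 at 5% flat and 0.56 to 0.86 at 30%. These figures rest on assumed flat rates and a pilot AUC that may not carry over to acceleration time. They show that the choice of rule matters, not how large any actual distortion would be.

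**What to change.** Amend SAP 7.1.3, 7.4 and 7.8 before outcomes are examined:

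1. Define acceleration time and state what a flat trace receives.
2. Do not treat a quality-confirmed pulseless recording as missing. Flag it from the stored waveform by a fixed criterion, masked to ABI, TBI, symptoms and cohort. The documents do not show that the waveform-fidelity entry on the CRF separates flat from failed recordings. Protocol 9.6 also keeps the best available record after five or more poor attempts, so failed recordings are stored too.
3. Report each ROC analysis three ways: with these limbs at a pre-specified tied most-diseased rank, with them at the opposite extreme, and complete-case. The scoring that may raise the AUC then does not stand alone.
4. Exclude only technical failures, at limb level, and use the same unit in all sections.
5. Report pulseless and failed recordings by disease group and visit.

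The cost is a few SAP sentences, a written flatness criterion and one masked pass over the stored toe recordings: about 240 × 3 + 160 = 880 at target limb numbers with full follow-up. There is extra derivation and validation, and three sets of results instead of one. No visits or subjects are added.

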7.3 Center Pooling

The analysis will use the pooled data from all centers because the marginal results are of primary interest.

7.4 Handling of Missing, Unused, and Spurious Data and Dropouts

Data that is missing or incomplete will not be imputed. Complete case data will be used where all data for the respective analysis is available for a patient or visit.

7.5 Adjustments for Multiple Comparisons

No adjustments will occur for multiple comparisons. A significance level of 0.05 will be used for all analyses and 95% CI will be computed.

7.6 Demographic and Other Baseline Characteristics

Demographic and baseline characteristic variables will be summarized descriptively. The mean, standard deviation, median, minimum, 1st quartile, 3rd quartile, maximum, and the corresponding number of participants or limbs will be reported for continuous variables. The percentage and count will be reported for categorical and binary variables.

7.7 ABI and TBI Values

The ABI and TBI for a limb will use the value in the data. If the ABI or TBI is missing, it will be derived from the ankle and brachial pressures or the toe and brachial pressures, respectively.

7.8 Acceleration Time Values

Acceleration time will be derived by the Research and Development Team based on data from the FlowMet device. Data should be merged based on the subject identifier, visit (0, 3, or 6 months), and limb.

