12.1.2 FlowMet-R data analysis and diagnostic model

FlowMet-R data is comprised of continuous blood flow data recorded over 30 seconds. Over this time, a pulsatile blood flow waveform may be present due to the subject's cardiac cycle, provided that digital blood flow is sufficient to generate such a signal. Thus, a combination of the flow amplitude and one or more features of the waveform may be used as inputs to train the predictive model.

The target outcome variable for training the model shall be a continuous metric of PAD severity, analogous to the ABI or TBI. The training will be performed as a regression using iterative algorithms ubiquitous in machine learning.

The predicted outputs from the regression model will be used to generate an ROC curve by classifying a binary diagnostic (i.e. PAD true/false, CLI true/false), or prognostic (i.e. vascular intervention likely within 6 months (true/false)). The classification algorithm which results in the highest diagnostic area under the curve for PAD and CLI shall be chosen to compute final sensitivity and specificity.

A k-fold cross validation scheme will be implemented to gauge model generalization. k-fold cross validation is a statistical sampling method that can be used to train and objectively validate the above

classification algorithms [34]. Using this scheme, only a subset of the total body of collected data is used to train the model, which is then applied to the remaining data withheld from training prospectively. During this validation stage, the performance and generalizability of the model can be assessed. Cross validation allows more objective selection of the optimal algorithm because performance assessment is based upon applying the model to a data set which it is naïve to (i.e. a prospective application of the model).

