7.10 Evaluation of Objectives

7.10.1 Primary Objectives

The primary objectives will compare the 95% CI of the AUC from the ROC curve to a value of 0.5 at 0-, 3-, and 6-months for the two definitions of PAD and one definition of CLI using the acceleration time from the FlowMet-R device. The 95% CI will not be corrected for repeated measures within a participant. If the 95% CI of the AUC excludes 0.5 at all time points for PAD or CLI, the acceleration time from the FlowMet-R device will be considered predictive of the respective endpoint. The 95% CI of the AUC will be derived using the method described in DeLong, et al (1998) [15]. Note, the definition of PAD will be defined two ways and analyzed separately. Definitions of PAD and CLI are provided in Section 4.1.1.1.1.

Three supplementary summaries will be computed. The sensitivity and specificity will be computed by selecting the point on the ROC curve closest to the upper left corner. Accuracy will be computed as the number of limbs correctly diagnosed divided by the total number of limbs.

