7.12 Changes to Planned Analysis

Patients will be classified based on definitions in Section 4.1.1.1.1 no matter the cohort they were originally enrolled in for the study.

8. Validation Requirements

To ensure the quality of the statistical results and datasets created for the study, the following validation requirements will be implemented. Programs that contribute directly or indirectly to the results pertaining to the primary and secondary objectives including TLG (Tables, Listings, and Graphs) development will be validated at least at level II by a statistician or a statistical programmer. Level I validation consists of a statistician or statistical programmer reviewer who independently programs output and then compares the output with that generated by the original statistician or statistical programmer according to the current work instruction. Level II: The peer reviewer reviews the code; where appropriate, performs manual calculations or simple programming checks to verify the output. Level III validation may be used for any previously validated program where only minor/administrative changes were made (e.g., change the location of the data directory). For level III validation, the original statistician or statistical programmer performs a visual inspection of the code and output to confirm functionality according to the current work instruction. Any results that are used for external publication or reports should be validated at levels I.

9. References

1. Mosely, L.H. and F. Finseth, Cigarette smoking: impairment of digital blood flow and wound healing in the hand. *The Hand*, 1977(2): p. 97-101.
2. Stadelmann, W.K., A.G. Digenis, and G.R. Tobin, Impediments to wound healing. *The American journal of surgery*, 1998. 176(2): p. 39S-47S.
3. Cronberg, C., et al., Peripheral arterial disease. *Acta Radiologica*, 2003. 44(1): p. 59-66.
4. Ouriel, K., Peripheral arterial disease. *The lancet*, 2001. 358(9289): p. 1257-1264.
5. Falanga, V., Wound healing and its impairment in the diabetic foot. *The lancet*, 2005. 366(9498): p. 1736-1743.
6. Norgren, L., et al., Inter-society consensus for the management of peripheral arterial disease (TASC II). *European Journal of Vascular and Endovascular Surgery*, 2007. 33(1): p. S1-S75.

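### The SAP leaves acceleration time, the only index-test value in the primary AUC rule, to the Research and Development team, with no definition, algorithm lock or masking to diagnosis stated.

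*SAP*

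**What the plan says.** Protocol 12.1.2 plans a model trained on flow amplitude and waveform features. On the choice of algorithm it says "The classification algorithm which results in the highest diagnostic area under the curve for PAD and CLI shall be chosen", with k-fold cross-validation as the check on optimism.

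The SAP narrows this to one feature. SAP 7.2 says the model value "will be derived by the Research and Development team and will consist of the acceleration time", and SAP 7.8 repeats that "Acceleration time will be derived by the Research and Development Team based on data from the FlowMet device", to be merged by subject, visit and limb. SAP 7.10.1 then builds the primary analysis "using the acceleration time from the FlowMet-R device" and sets a pass rule: "If the 95% CI of the AUC excludes 0.5 at all time points for PAD or CLI", acceleration time is to be called predictive of that endpoint. SAP 7.5 adds: "A significance level of 0.05 will be used for all analyses and 95% CI will be computed".

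SAP 7.12, the section for changes to the planned analysis, has a single entry: "Patients will be classified based on definitions in Section 4.1.1.1.1 no matter the cohort they were originally enrolled in for the study". The move from the protocol's model to acceleration time is not listed there, and cross-validation does not appear in the SAP.

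The masking that is stated (protocol 5 and 9.8) concerns the treating physician and site staff, who do not see FlowMet-R outputs during interventional procedures.

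**The concern.** A waveform feature is not read off the device without decisions. Someone must choose which beats count, how artefacts are removed, where the foot and peak lie, and what to do when there is hardly any pulse. Protocol 9.6 says that in advanced disease the waveform may be severely damped or missing. It also lets the clinician pick the best record once five or more attempts have given poor data. No rule says how acceleration time is obtained from such traces, or whether the limb becomes missing and drops out under the complete-case rule of SAP 7.4. These decisions fall mostly on the most diseased limbs, so they are tied to the diagnosis being tested.

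If the people making them know the diagnosis, or can revise the algorithm after seeing how it separates the groups, the AUC can move away from 0.5 for reasons unrelated to the device. The DeLong interval does not reflect this. The same derivation would also act at months 0, 3 and 6, so requiring success at all three visits gives limited protection against it.

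**Working it through.** The plan gives no figure on this point, so there is none to reproduce. The reference value is nominal: with a two-sided 95% interval, a worthless marker has a chance of 0.025 per visit that the lower limit exceeds 0.5.

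**Safeguards in the documents**

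| Safeguard | Where | What it protects |
|---|---|---|
| Site staff masked to FlowMet-R output | Protocol 5, 9.8 | Conduct of the intervention |
| Recording taken before ABI/TBI | Protocol 9.6 | Acquisition |
| Signal-quality checks | Protocol 9.6 | Acquisition |
| Program validation, at least level II | SAP 8 | Correctness of code |
| Merge by subject, visit and limb | SAP 7.8 | Correct linkage; says nothing of what the team knew beforehand |

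None covers the step from recording to acceleration time.

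**Illustration 1: label-aware processing, baseline only**

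Inputs: 240 PAD and 160 control limbs (SAP 6), and assumed shifts d of 0.1, 0.2 and 0.3 SD in a marker with no true value.

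- AUC: A = Φ(d/√2).
- Hanley-McNeil: SE² = [A(1−A) + 239(P₁−A²) + 159(P₂−A²)]/(240×160), with P₁ = A/(2−A) and P₂ = 2A²/(1+A).
- Chance that the lower limit exceeds 0.5: Φ((A−0.5)/SE − 1.96).

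| Shift (SD) | AUC | SE | (A−0.5)/SE | Chance |
|---|---|---|---|---|
| 0.1 | 0.528 | 0.0293 | 0.961 | 0.16 |
| 0.2 | 0.556 | 0.0291 | 1.936 | 0.49 |
| 0.3 | 0.584 | 0.0287 | 2.931 | 0.83 |

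The calculation treats limbs as independent, as SAP 7.10.1 does. It does not carry over to months 3 and 6, because healthy subjects are measured once (protocol 5, SAP 5) and the number of negative limbs at those visits is not given.

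**Illustration 2: choosing among candidate derivations**

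Null scores were simulated with DeLong intervals (1,500 runs per cell; 240 v 160 and 100 v 160 limbs), keeping the highest AUC. The number of candidates and their correlation (0, 0.5 or 0.8) are assumptions.

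| Candidates | Per-visit chance that lower limit exceeds 0.5 | Mean AUC kept |
|---|---|---|
| 1 (locked) | 0.020–0.027 | about 0.50 |
| 3 | 0.045–0.074 | 0.511–0.531 |
| 5 | 0.063–0.132 | 0.516–0.543 |
| 10 | 0.085–0.245 | 0.521–0.557 |

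For the best of 10, normal theory gives 1 − 0.975¹⁰ = 0.22 if the candidates are independent, and simulation gives 0.14 at correlation 0.5.

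Under the actual rule, a feature picked at baseline must also succeed at months 3 and 6. With the best of 10 null features, the chance of success at all three visits is below 0.001 if visits are independent. At between-visit correlation 0.5 it is about 0.014 (independent features) or 0.010 (feature correlation 0.5), and at 0.8 about 0.07 or 0.04.

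**The case against.** The SAP is tighter than the protocol: it names one feature where the protocol allowed several and would have picked the algorithm with the highest AUC. The switch is openly stated in SAP 7.2, so its absence from 7.12 is partly a bookkeeping gap. Recordings precede ABI and TBI, quality criteria apply at acquisition, and acceleration time arrives as separate data to be merged. All of this is true and limits the room for bias. But naming a feature does not fix its computation, and none of these steps keeps diagnosis from the people who derive the value.

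SAP 7.2 also calls the objectives descriptive. SAP 7.10.1 nonetheless attaches a conclusion to the interval.

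Three stronger readings are tempting and not supported:

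- A reader might infer that the team is unmasked and the algorithm unlocked. The documents support only that neither safeguard is stated. Some SAP pages are not available, the event schedules are figures not shown, and device specifications may lie elsewhere. That the team belongs to the sponsor is likewise an inference; SAP 7.2 says only "Data analysis will be performed by Medtronic employed statisticians/programmers".
- A reader might infer that acceleration time was selected on this trial's limbs. Nothing shows this, and nothing rules it out.
- A reader might put the selection error at 0.40 (1 − 0.95¹⁰), or 0.29 at correlation 0.5. Those count departures in either direction at a single visit. Keeping the highest AUC and counting the high side gives 0.22 and 0.14, and the all-visits rule lowers this further.

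**Conclusion.** The point stands as a gap in the SAP that should be closed. One value carries the primary rule, its derivation involves judgement in the most diseased limbs, and no definition, version, lock or masking is stated.

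The larger risk is label-aware derivation, because it would persist across visits: 0.16 to 0.83 at baseline against 0.025, if the shift is 0.1 to 0.3 SD. Those shifts have no basis in the documents and show sensitivity only. Selection of the feature itself is unresolved; under the rule as written its effect would be about 0.07 or less, for ten null candidates and between-visit correlations up to 0.8. No bias is shown to have occurred.

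**What to change.** In SAP 7.8:

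1. Define acceleration time: beat selection, averaging, artefact handling, and what is done with damped or absent waveforms, including when the value is set to missing.
2. Name the algorithm version and freeze it before any waveform is linked to clinical data.
3. Give the Research and Development team coded recordings without cohort, ABI, TBI, Rutherford class, wound status or outcome. The team returns one value per recording, and the trial statistician does the merge.

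In SAP 7.12, record the change from the cross-validated model of protocol 12.1.2 to acceleration time, with the date of the choice and the data it was made on. If it was made on this trial's limbs, label the AUC exploratory.

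The cost is SAP wording and a coded file transfer; sample size does not change. The one drawback is that processing questions can no longer be settled by looking at the clinical record.
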